### 9.2.3 Analysis of Exploratory Outcome Measures

The exploratory efficacy endpoints are:

Alanine transaminase (ALT) at week 14

Aspartate transaminase (AST) at week 14

Total bilirubin at week 14

Triglycerides at week 14

## STATISTICAL ANALYSIS PLAN (SAP) CD1-NASH-01

Protocol No. CD1-NASH-01	Revision No. Rev. 00	Effective Date: 17-Dec-2021
-----------------------------	-------------------------	--------------------------------

Density Lipoprotein (LDL) at week 14

### *Analysis of Continous Exploratory Endpoints*

Change from baseline to Week 14 in the continuous exploratory endpoints will be analyzed using methods like the one used for the primary endpoint.

#### 9.2.4 Analysis of CCR5 Biomarkers that may Predict Activity of Leronlimab

To examine if monocyte/T cell CCR5 biomarker is predictive of leronlimab activity, the statistical significance of biomarker and treatment group interaction group will be assessed. The change from baseline to Week 14 in MRI-PDFF (and cT1) will be regressed on biomarker and treatment group and their interaction as covariables. The p-values for these effects will be presented:

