Urine samples will be tested for color, appearance, specific gravity, pH, protein, glucose, occult blood, ketones, leukocyte esterases, nitrites, bilirubin, urobilinogen. Microscopic examination of urine sediment will be performed if there are abnormalities in macroscopic urinalysis results. Microscopic urine tests include bacteria, cast, crystals, epithelial cells, RBC and WBC.

All laboratory reports will be reviewed by the Investigator. Abnormal results that are considered by the Investigator to be clinically significant will be recorded as adverse events. In order to make the determination of clinical significance the testing may be needed to be repeated as per Investigator's judgement. Validated, quality-controlled laboratory data will be transferred to the main database for analyses.

Table 7-1: Central Lab Parameters

CBC Parameters	Biochemistry Parameters	Urinalysis
Hemoglobin	Liver Function Tests / NASH Markers	pH
Hematocrit	Total Bilirubin	Appearance
RBC count	Direct Bilirubin	Color
WBC count	Alkaline Phosphatase (ALP)	Specific gravity
WBC Differential	Alanine Aminotransferase (ALT) (or SGPT)	Turbidity
Absolute lymphocyte count	Aspartate Aminotransferase (AST) (or SGOT)	Ketones
Absolute neutrophil count	Prothrombin Time (PT)	Bilirubin
Platelet count	International Normalized Ratio (INR)	Blood
Serology		Glucose
HBs Ag, HCV Ab and HCV RNA (if required), HAV Ab, HEV Ab, HIV Ag	Albumin	Protein
Miscellaneous		Nitrites
Serum pregnancy test	Triglycerides	Urobilinogen
Urine pregnancy test (for female subjects of childbearing potential)	Cholesterol (Low density lipoprotein)	Leukocyte esterases
Anti-Drug Antibodies (ADA) to PRO 140	Creatine kinase	Note: Microscopic examination of urine sediment will be performed if there are abnormalities in macroscopic urinalysis results. Microscopic urine tests include bacteria, cast, crystals, epithelial cells, RBC and WBC.
PK evaluations	Gamma-glutamyltransferase (GGT)	
Monocyte/T cell CCR5 biomarker assay	Serum CK-18	
Pro-inflammatory Biomarkers		
IL-1 alpha, IL-1 beta, IL-6, RANTES (CCL5), TNF-alpha, TNF-beta, CRP	Renal Function Tests blood urea nitrogen (BUN)	
FibroTest		
Gamma-glutamyltransferase* Total bilirubin* Alpha-2-macroglobulin Apolipoprotein A1 Haptoglobin. ALT*	Creatinine eGFR Electrolytes Sodium Potassium Chloride Calcium Bicarbonate Other: Fasting Blood Glucose Serum HbA1c Thyroid profile	
*Part of Liver Function Tests Panel		

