8.2 STUDY OUTCOME MEASURES

Primary Efficacy Outcome Measure:

- Change from baseline in hepatic fat fraction assessed by magnetic resonance imaging-derived proton density fat fraction (MRI-PDFF) at week 14

Secondary Efficacy Outcome Measures:

- Change from baseline in fibro-inflammatory activity as assessed by cT1 (corrected T1) assessed by multiparametric magnetic resonance imaging (MRI) of liver at week 14

Note: cT1 measured in milliseconds (ms) is a quantitative metric for assessing a composite of liver inflammation and fibrosis

- Change from baseline in liver fibrosis using FibroTest at week 14
- Change from baseline in hepatic inflammatory activity using FibroTest at week 14
- Change from baseline in serum pro-inflammatory biomarkers assessments
- Change from baseline in Gamma-glutamyltransferase (GGT) at week 14
- Change from baseline in CK-18 level at week 14
- Change from baseline in Leronlimab (PRO 140) PK assessments

Exploratory Outcome Measures:

- Change from baseline in Alanine transaminase (ALT) at week 14
- Change from baseline in Aspartate transaminase (AST) at week 14

- Change from baseline in total bilirubin at week 14
- Change from baseline in triglycerides at week 14
- Change from baseline in Low Density Lipoprotein (LDL) at week 14
- To explore Monocyte/T cell CCR5 biomarkers that may predict activity of leronlimab.

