### 3.3 Exploratory Endpoints

The exploratory endpoints for Part 1 of the study are

- The fibrosis scores categorized by degree of liver fibrosis as per cT1 value:
  - Mild 800-850 cT1
  - Moderate 851-999 cT1
  - Mild-Moderate 800-999 cT1
  - Severe  $\geq 1000$  cT1
- Change from baseline in Alanine transaminase (ALT) at week 14
- Change from baseline in Aspartate transaminase (AST) at week 14
- Change from baseline in total bilirubin at week 14
- Change from baseline in triglycerides at week 14
- Change from baseline in Low Density Lipoprotein (LDL) at week 14
- Change from baseline in High Density Lipoprotein (HDL) at week 14
- To explore Monocyte/T cell CCR5 biomarkers that may predict activity of leronlimab.

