#### Summary of Biomarker as a Predictive Factor PART 1\*

**	p-value		
	Bio-marker	Treat-ment	Inter-action
Pro-inflammatory Biomarkers	0.xxx	0.xxx	0.xxx
IL-1 alpha	0.xxx	0.xxx	0.xxx
IL-1 beta	0.xxx	0.xxx	0.xxx
IL-6	0.xxx	0.xxx	0.xxx
RANTES (CCL5)	0.xxx	0.xxx	0.xxx
TNF-alpha	0.xxx	0.xxx	0.xxx
TNF-beta	0.xxx	0.xxx	0.xxx
CRP	0.xxx	0.xxx	0.xxx
Fibro Test			
Gamma-glutamyltransferase	0.xxx	0.xxx	0.xxx
Total bilirubin	0.xxx	0.xxx	0.xxx
Alpha-2-macroglobulin	0.xxx	0.xxx	0.xxx
Apolipoprotein A1	0.xxx	0.xxx	0.xxx
Haptoglobin.	0.xxx	0.xxx	0.xxx
ALT	0.xxx	0.xxx	0.xxx
Liver Function Tests / NASH Markers	0.xxx	0.xxx	0.xxx
Total Bilirubin	0.xxx	0.xxx	0.xxx
Direct Bilirubin	0.xxx	0.xxx	0.xxx
Alkaline Phosphatase (ALP)	0.xxx	0.xxx	0.xxx
Alanine Aminotransferase (ALT) (or SGPT)	0.xxx	0.xxx	0.xxx
Aspartate Aminotransferase (AST) (or SGOT)	0.xxx	0.xxx	0.xxx
Prothrombin Time (PT)	0.xxx	0.xxx	0.xxx
International Normalized Ratio (INR)	0.xxx	0.xxx	0.xxx
Albumin	0.xxx	0.xxx	0.xxx
Total Protein	0.xxx	0.xxx	0.xxx
Triglycerides	0.xxx	0.xxx	0.xxx
Cholesterol (Low density lipoprotein)	0.xxx	0.xxx	0.xxx
Cholesterol (High density lipoprotein)	0.xxx	0.xxx	0.xxx

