## 10 CHANGES IN SAP COMPARED TO STUDY PROTOCOL

### 10.1 Addition of Exploratory Outcome Measures

After finalization of the protocol, following outcome measures were added to the list of exploratory outcome measurements.

Efficacy outcome parameters by a CCR5 Haplotype biomarker :

- Change from baseline in hepatic fat fraction assessed by magnetic resonance imaging-derived proton density fat fraction (MRI-PDFF) at week 14 by CCR5 Haplotype biomarker
- Change from baseline in fibro-inflammatory activity as assessed by cT1 (corrected T1) assessed by multiparametric magnetic resonance imaging (MRI) of liver at week 14 by CCR5 Haplotype biomarker

Efficacy outcome parameters by a CCR5 calcium flux biomarker :

- Change from baseline in hepatic fat fraction assessed by magnetic resonance imaging-derived proton density fat fraction (MRI-PDFF) at week 14 by CCR5 calcium flux biomarker
- Change from baseline in fibro-inflammatory activity as assessed by cT1 (corrected T1) assessed by multiparametric magnetic resonance imaging (MRI) of liver at week 14 by CCR5 calcium flux biomarker

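### SAP 9.2.4 plans a CCR5 predictive-marker test, but the table that is to report it has no row for the CCR5 assay, haplotype or calcium flux

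*SAP*

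**What the plan says.** The last exploratory outcome measure in Protocol 8.2 is "To explore Monocyte/T cell CCR5 biomarkers that may predict activity of leronlimab". Table 7-1 of the protocol lists the CCR5 assay as its own item, apart from the pro-inflammatory, FibroTest and biochemistry panels. Protocol 7.9 schedules it at T1 before the first dose, T2, T6, T10, EOT/ET and follow-up. Footnote 21 of the schedule lets subjects who have already finished EOT/ET and follow-up give the sample at an unscheduled visit.

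SAP 9.2.4 states its purpose as "To examine if monocyte/T cell CCR5 biomarker is predictive of leronlimab activity". Change in MRI-PDFF (and cT1) "will be regressed on biomarker and treatment group and their interaction as covariables", and the p-values are to appear in the table that follows. That table is headed as a summary of biomarkers as predictive factors. It groups its rows under pro-inflammatory markers, FibroTest, and liver function/NASH markers. One programming note asks for a Part 2 repeat using the Part 1 placebo group; another asks that the list be adjusted to the laboratory data actually obtained.

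SAP 10.1 adds "Efficacy outcome parameters by a CCR5 Haplotype biomarker" and a matching item for CCR5 calcium flux, each for MRI-PDFF and cT1.

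SAP 3.3 includes "Change from baseline in High Density Lipoprotein (HDL) at week 14", and the 9.2.4 table has a row beginning "Cholesterol (High density lipoprotein". The only cholesterol fraction in protocol Table 7-1 is the entry beginning "Cholesterol (Low density lipoprotein".

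**The concern.** The text of 9.2.4 asks about one marker and its table reports on others. A programmer working from the table would produce interaction p-values for albumin, INR or IL-6 and none for the assay drawn to answer the question. A nominally significant row would then sit in a section whose heading is about CCR5 prediction.

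The plan also does not define the CCR5 variable. It does not say which readout or cell type is meant, or whether the predictor is the pre-dose value, a later value or a change. That matters because footnote 21 admits samples taken after study completion, and a value measured after treatment is not a baseline predictor. If these choices are made after unblinding, the analysis is no longer pre-specified.

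Two smaller faults sit in the same table. Three assays are printed twice, and HDL appears without a listed measurement.

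**Working it through.** The documents give no figure for this analysis, and the sample size rests on clinical judgment, so there is nothing of the plan's own to reproduce. The check is a row count, a comparison with the protocol's lab list, and simple multiplicity arithmetic.

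**Row count, SAP 9.2.4 table**
- Pro-inflammatory: IL-1 alpha, IL-1 beta, IL-6, RANTES (CCL5), TNF-alpha, TNF-beta, CRP = 7
- FibroTest: GGT, total bilirubin, alpha-2-macroglobulin, apolipoprotein A1, haptoglobin, ALT = 6
- Liver/NASH: total and direct bilirubin, ALP, ALT, AST, PT, INR, albumin, total protein, triglycerides, LDL, HDL, creatine kinase, GGT, CK-18 = 15
- Total: 7 + 6 + 15 = 28

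**CCR5 rows:** 0 of 28 for the cell assay, haplotype or calcium flux. The nearest is RANTES (CCL5), which Protocol 1.2 describes as a CCR5 ligand and Table 7-1 files with the serum pro-inflammatory markers.

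**Repeats:** GGT, total bilirubin and ALT appear under both FibroTest and liver tests. Table 7-1 stars these three FibroTest items as "Part of Liver Function Tests Panel", so each pair is one measurement. Distinct markers: 28 - 3 = 25.

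**HDL:** in SAP 3.3 and the 9.2.4 table. It is absent from the protocol's exploratory list (8.2), schedule footnote 11, Table 7-1, SAP 9.2.3 and SAP 10. Distinct markers on the protocol's lab list: 25 - 1 = 24.

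**Chance findings.** Let m be the number of interaction tests, each at 0.05 (SAP 9.1; no multiplicity adjustment is stated). If no interaction is real, the expected number below 0.05 is 0.05m, whatever the correlation between tests. The chance of at least one is 1 - 0.95^m under independence only. The counts take one analysis set and two outcomes.

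| Rows counted | m per part | Expected below 0.05 | P(at least one), if independent |
|---|---|---|---|
| 28 as printed | 28 x 2 = 56 | 2.8 | 0.94 |
| 25 distinct | 25 x 2 = 50 | 2.5 | 0.92 |
| 24 distinct, without HDL | 24 x 2 = 48 | 2.4 | 0.91 |
| 3 CCR5 markers only | 3 x 2 = 6 | 0.3 | 0.26 |

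The last row assumes one variable each for the cell assay, haplotype and calcium flux; the documents do not give the number. If monocyte and T cell readouts are tested separately there are 4 markers, so 4 x 2 = 8 tests and 8 x 0.05 = 0.4 expected. Over both parts the printed table gives 56 x 2 = 112 tests and 5.6 expected. The right-hand column is illustrative, because liver labs are correlated, repeated rows are identical, and the two parts share a placebo group.

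**Model.** As written, the 9.2.4 regression has marker, treatment and interaction but no baseline value of the outcome. SAP 9.1.2 says baseline values are used as a covariate in efficacy analyses.

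**The case against.** The best defence is that 9.2.4 does plan the analysis: it names the CCR5 marker, both outcomes and an interaction model. The note to adjust the list can be read as allowing additions, and the CCR5 assay is among the protocol's central laboratory items. SAP 9.1.1 leaves the formal table shells to a separate document that is not available here. SAP 10.1 names the same two outcomes as 9.2.4, whose heading is plural, so haplotype and calcium flux may be meant to use the same model.

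Much of this stands, and it rules out several stronger readings that a reader might infer:
- That the CCR5 question has no planned test or will go unanswered. The text of 9.2.4 commits to a test.
- That a study objective is at risk. The objectives in Protocol 2 and SAP 2.1 do not mention CCR5; this is an exploratory outcome measure.
- That HDL cannot be obtained. The documents show only that it is not listed; biochemistry blood is drawn at T1 and EOT, and the laboratory manual is not available here.
- That 90 x 6 = 540 CCR5 samples are left without a test. That product is a ceiling, since footnote 21 implies that some subjects lack the full series, and the planned test covers the assay.
- That the repeated rows distort results. They print the same p-value twice.

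The defence does not supply the missing definition. Permission to adjust a list does not tell a programmer which CCR5 readout, cell type or visit to use, and nothing links SAP 10.1 to 9.2.4.

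**Conclusion.** The point holds as a mismatch between text and table. SAP 9.2.4 commits to a CCR5 interaction test, but its table lists 28 rows of other markers and none for the CCR5 assay, haplotype or calcium flux. The CCR5 predictor itself is undefined. Followed as printed, each part would show 56 nominal interaction tests, with about 2.8 expected below 0.05 if no interaction is real, under a CCR5 heading and without the CCR5 result. This rests on reading the table as repeated for MRI-PDFF and cT1 and on counting one analysis set.

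The repeated assays are cosmetic. HDL is a separate small inconsistency: an endpoint in SAP 3.3 with no listed measurement and no entry among the SAP's changes. The whole point is minor, because the outcome is exploratory and the primary and secondary analyses are unaffected.

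**What to change.** Revise SAP 9.2.4 and its table before unblinding:

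1. Add rows for the monocyte/T cell CCR5 readouts, naming each readout and cell type. Use the pre-dose T1 value as the predictor, and report how many subjects per group have one, given footnote 21.
2. Add rows for CCR5 haplotype and calcium flux. Cross-refer SAP 10.1 to the same marker-by-treatment model for PDFF and cT1.
3. Put the baseline value of the outcome into that model, in line with SAP 9.1.2.
4. Move the cytokine, FibroTest and liver-lab rows to a separate table labelled exploratory, non-CCR5 and unadjusted for multiplicity. Print GGT, total bilirubin and ALT once. This does not reduce the number of chance findings; it stops them being read as CCR5 results.
5. Delete HDL from SAP 3.3 and 9.2.4. If the central laboratory did report it at baseline and week 14, record it instead in SAP 10 as a change from the protocol and list it in 9.2.3.

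The cost is SAP and table-shell wording, with no new samples. The downsides are that HDL may be dropped, and that subjects without a pre-dose CCR5 sample would not contribute to the CCR5 assay rows.

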- [12] Urine samples will be tested for pH, appearance, color, specific gravity, turbidity, ketones, bilirubin, occult blood, glucose, protein, nitrites, urobilinogen, and leukocyte esterases. Microscopic examination of urine sediment will be performed if there are abnormalities in macroscopic urinalysis results. Microscopic urine tests include bacteria, cast, crystals, epithelial cells, RBC and WBC.
- [13] Only performed on women of childbearing potential
- [14] Blood sample collected at T1 (prior to first dose of PRO 140), pre-dose at T2, T6, T10, and at EOT (or ET) and Follow-up visit
- [15] Randomization via WebView CTMS system only applicable for Part 1 of the study
- [16] Leronlimab (PRO 140) or placebo is administered as subcutaneous injection in the abdomen weekly. In Part 1 of the study, a total of 700 mg dose of leronlimab (PRO 140) or placebo will be delivered as two injections of 2 mL. In the Part 2 of the study, a total dose of 350 mg dose of leronlimab (PRO 140) will be delivered as one injection of 2 mL.
- [17] Injection Site Reaction Assessment as assessed by Investigator (or designee) at the clinic .
- [18] Subject-perceived injection site pain (average pain since last treatment) will be assessed using 11-point Numeric Rating Scale from 0 to 10 prior to each study treatment administration. "0" meaning "no pain" and "10" meaning "worst possible" pain.
- [19] AE and CM evaluations to be conducted at each clinic visit applicable
- [20] Subjects discontinuing the study at any time for any reason (early termination-ET) should complete the procedures listed AND the follow-up visit
- [21] In case subjects have already completed their EOT/ET and FU visits, site should use the Unscheduled Visit option to collect blood sample for Monocyte/T Cell CCR5 analysis.

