Note: For the purpose of the assessment of drug-induced liver injury (DILI), Baseline Measurements (BLM) for lab values (such as AST, ALT, total Bilirubin) refers to the average (mean) value of Screening Visit (SV) and T1 Visit. If liver function tests are repeated during Screening Phase, the average (mean) value of all Screening Visit tests and T1 Visit will be used to calculate the Baseline Measurements.

All data normally collected at the scheduled EOT Visit should be recorded at the time of premature discontinuation.

If a subject fails to return for the scheduled study visit or is discontinued from the study, an attempt will be made to determine the reason(s). If the subject is unreachable by telephone, a registered letter will be sent to the subject requesting that he/she contact the clinic.

All patients with an ongoing SAE at the Post-Study (Follow-up) Visit (scheduled or premature) must be followed until the event is resolved (with or without sequelae) or deemed stable.

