7.9 CLINICAL LABORATORY ASSESSMENTS

Blood samples will be collected for analysis of the following parameters:

- Hematology (Complete Blood Count) will be performed at SV, T1 (prior to first dose), T2, T6, T10, EOT/ET visits.
- Biochemistry will be performed at SV, T1 (prior to first dose), T2, T6, T10, EOT/ET and FU visits.

Note: Screening laboratory test can be repeated once during the 28-day screening window based on the Investigator's clinical judgement).

- Serum pro-inflammatory biomarkers including IL-1 alpha, IL-1 beta, IL-6, RANTES (CCL5), TNF-alpha, TNF-beta, CRP will be performed at T1 (prior to first dose), T2 (pre-dose), T6 (pre-dose), T10 (pre-dose), EOT/ET and FU visits.
- FibroTest (requires fasting for 12 hours or more) combines 5 standard biomarkers (gamma-glutamyltransferase, total bilirubin, alpha-2-macroglobulin, apolipoprotein A1, and haptoglobin). The Acti-Test adds a marker for inflammatory activity (alanine aminotransferase: ALT). FibroTest will be performed at SV, T1 (prior to first dose), T2, T6, T10, EOT/ET visits.
- Serology tests including HBs Ag, HCV Ab and HCV RNA (only performed if HCV Ab is positive), HIV Ab, Hepatitis A and Hepatitis E Abs will be performed at SV.
- Anti-Drug antibodies (ADA) to PRO 140 at T1 (prior to first dose), T2 (pre-dose), T6 (pre-dose), T10 (pre-dose), EOT/ET and FU visits.
- PK assessment at T1 (prior to first dose), T2 (pre-dose), T6 (pre-dose), T10 (pre-dose), EOT/ET and FU visits.

- Serum pregnancy test (for female subjects of childbearing potential) at SV.
- Monocyte/T cell CCR5 biomarker assay at T1 (prior to first dose), T2 (pre-dose), T6 (pre-dose), T10 (pre-dose), EOT/ET and FU visits.

Note: In case subjects have already completed their EOT/ET and FU visits, site should use the Unscheduled Visit option to collect blood sample for Monocyte/T Cell CCR5 analysis.

Urine samples will be collected for analysis of the following parameters:

- Urine pregnancy at T1 (prior to first dose), T6, T10, EOT/ET visits.

Note: A urine sample will be collected from female subjects of childbearing potential. This test will be performed at the study site using a commercially available kit.

- Urine analysis testing at SV, T1 (prior to first dose), T2, T6, T10, EOT/ET visits.

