8.7 GENERAL STATISTICAL CONSIDERATIONS

All collected study data will be presented in subject data listings. Statistical analyses will be performed using SAS® for Windows, version 9.4 or later. Descriptive statistics (n, mean, standard deviation, median, minimum and maximum) will be presented by treatment group for continuous variables. Frequencies and percentages will be presented by treatment group for categorical variables.

Analysis Populations

Intent-to-Treat Population

The **Intent-to-Treat (ITT) population** is defined as the set of subjects who have received at least one dose of study treatment (Leronlimab (PRO 140) or placebo) and have at least one post-baseline efficacy assessment. The ITT population will be used as the primary analysis population.

Per Protocol Population

The **Per Protocol (PP) population** is defined as the set of subjects who meet the ITT population requirements, were not associated with any major protocol violations and have at least 80% of compliance with study treatment. This population will be identified before the database lock.

The PP analysis of primary and secondary endpoints will be considered supportive.

Safety Population

The **Safety Population** will include all subjects who have received one dose of study treatment (Leronlimab (PRO 140) or placebo). This population will be used for the analysis of safety parameters.

Covariates

For efficacy analyses, the baseline values will be used as covariates in the analysis models. Other important prognostic factors will be specified in the SAP for the study.

Missing Data

All data will be used as observed, and no imputations will be made for any missing data point for early phase study.

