#### 9.1.2 Covariates

For efficacy analyses the baseline values will be used as a covariate.

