### 9.2.1 Analysis of Primary Efficacy Endpoint

The null hypothesis of no between treatment group difference in mean change from baseline in hepatic fat fraction assessed by magnetic resonance imaging-derived proton density fat fraction (MRI-PDFF) at week 14 against alternate hypothesis of a non-zero treatment-difference will be tested at 0.05 level of significance.

A preliminary assessment of normality will be performed using Shapiro-Wilks test at the 5% significance level.

If departure from normality is not concluded a normality-based parametric test of the null hypothesis will be performed using ANCOVA with baseline as a continuous covariate and treatment group as a categorical covariate. The point estimate of the mean (SD) along with corresponding 95% confidence interval will be presented. The baseline adjusted estimates of the treatment means and treatment difference along with 95% confidence interval and the two-sided p-values will be presented.

Otherwise, the null hypothesis will be tested using the two-sample Wilcoxon Rank Sum test and the Hodges-Lehmann estimate of location shift along with the corresponding 95% confidence intervals will be reported.

Even if the parametric analysis is deemed appropriate, the non-parametric analyses will be performed to assess the robustness of the conclusions based on ANCOVA.

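### The exploratory predictive-marker model in SAP 9.2.4 does not carry in the baseline covariate required elsewhere and does not say which visit's marker value is used.

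*SAP*

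**What the plan says.** SAP 9.2.4 sits under SAP 9.2, the efficacy section. It specifies the model as follows: "The change from baseline to Week 14 in MRI-PDFF (and cT1) will be regressed on biomarker and treatment group and their interaction as covariables". The table shell prints p-values for marker, treatment and interaction, and a programming note repeats it for Part 2 against the Part 1 placebo group.

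On baseline, SAP 9.1.2 says: "For efficacy analyses the baseline values will be used as a covariate". Protocol 8.7 says the same: "For efficacy analyses, the baseline values will be used as covariates in the analysis models". SAP 9.2.1 writes the term into the primary model: "ANCOVA with baseline as a continuous covariate and treatment group as a categorical covariate".

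On timing, protocol 7.9 lists the CCR5 samples: "Monocyte/T cell CCR5 biomarker assay at T1 (prior to first dose), T2 (pre-dose), T6 (pre-dose), T10 (pre-dose"), followed by EOT/ET and follow-up. The cytokines and CRP share that schedule. For FibroTest, "FibroTest will be performed at SV, T1 (prior to first dose), T2, T6, T10, EOT/ET visits". Biochemistry is taken at those visits and at follow-up. Table 4-2 footnote 21 adds, for CCR5: "In case subjects have already completed their EOT/ET and FU visits, site should use the Unscheduled Visit option to collect blood sample".

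The documents define a laboratory baseline once, in the liver-injury note of protocol 5.1: "Baseline Measurements (BLM) for lab values (such as AST, ALT, total Bilirubin) refers to the average (mean) value of Screening Visit (SV") and T1. That definition is limited to the liver-injury assessment.

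**The concern.** A predictive marker has to be measured before treatment. If it is measured afterwards, the drug may already have moved it, and a marker-by-treatment interaction can then reflect response rather than prediction. SAP 9.2.4 does not name the visit, and the word pre-dose does not settle it, because the T2, T6 and T10 samples carry that label too.

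The baseline gap is separate. For the continuous secondary and exploratory endpoints, the SAP borrows the primary method, and with it the baseline term. Section 9.2.4 neither borrows that method nor names baseline. It gives its own list of terms, and a programmer following it literally would leave baseline out.

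At stake are the precision of the interaction test, the meaning of the marker p-value and, in the non-randomised Part 2 repeat, the treatment p-value. The primary analysis is not involved.

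**Working it through.** The plan states no power or precision figure for this analysis, and its sample size rests on clinical judgment, so there is no figure of its own to reproduce.

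**Visits (protocol 7.9), scheduled / before first dose.** CCR5 and cytokines 6 / 1 (T1). FibroTest 6 / 2 (screening, T1). Biochemistry 7 / 2 (screening, T1).

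**Shell rows (SAP 9.2.4).** 7 + 6 + 15 = 28. GGT, total bilirubin and ALT each appear twice, so there are 28 - 3 = 25 distinct analytes. None is a monocyte/T cell CCR5 row, although Programming Note 2 lets the list be adjusted.

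**Inputs.** 30 per arm (SAP section 4) and two-sided 0.05 (SAP 9.1). The documents give no correlations, so these are assumptions: baseline with change, rho = 0.2 to 0.5; marker with baseline, r = 0 to 0.5. Variables are in SD units. Simulations used 20,000 trials per setting and ordinary least squares. The hand formulas below use 1/(n-3) for the mean inverse sum of squares of a standard normal marker in one arm.

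**1. Precision of the interaction.** With the marker unrelated to baseline, SE is about s x sqrt(2/27), where s = 1 without baseline and s = sqrt(1-rho^2) with it.
- Without baseline: 0.272 (simulated 0.270).
- With baseline, rho 0.2: 0.980 x 0.272 = 0.267 (simulated 0.267).
- With baseline, rho 0.5: 0.866 x 0.272 = 0.236 (simulated 0.236).
- At r = 0.5 the simulated pairs are 0.269 to 0.267 (rho 0.2) and 0.261 to 0.236 (rho 0.5).

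The reduction is therefore about 1-13%. With equal baseline slopes in the two arms, interaction rejections under the null stay near 5% with or without baseline.

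**2. Marker p-value.** Suppose the marker adds nothing beyond baseline. Its placebo-arm slope without adjustment is then rho x r in size. At rho = r = 0.5 the slope is 0.25, the SE is sqrt(1-0.0625) x sqrt(1/27) = 0.186, the ratio is 1.34 and the rejection rate is about 27% (simulated 28.0%). Across rho 0.2-0.5 the simulated rates are 6-13% at r = 0.3 and 8-28% at r = 0.5, against about 5% with baseline in the model.

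**3. Post-dose marker.** Take a marker linked to response with correlation a in treated subjects and b in placebo subjects, every value being post-dose. The slope difference is a-b and its SE is about sqrt(((1-a^2)+(1-b^2))/2) x sqrt(2/27).

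| a / b | (a-b)/SE | Rejects, formula | Rejects, simulated |
|---|---|---|---|
| 0.3 / 0 | 1.13 | 20% | 20.5% |
| 0.4 / 0 | 1.53 | 33-34% | 33.2% |
| 0.5 / 0 | 1.96 | 50% | 49.6% |
| 0.4 / 0.2 | 0.77 | 12% | 12.1% |
| 0.5 / 0.3 | 0.81 | 13% | 12.9% |

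With equal links (0.3 to 0.5 in both arms) the interaction holds at 5%, but the marker column is significant in 37-84% of trials. With a treated-only link in 25% or 50% of subjects, the interaction rejects in 6-8% or 9-16%. A second construction, in which the drug moves both marker and PDFF, gave 7-50% with the post-dose value, 4-5% with the T1 value, and 5% where there was no link.

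**4. Part 2.** Assume a 0.5 SD baseline difference between the 350 mg group and the Part 1 placebo group. The bias in the treatment term is rho x 0.5. At rho = 0.5 and r = 0 this is 0.25 / sqrt(2/30) = 0.97, giving about 16% rejections. The simulated range over rho 0.2-0.5 and r 0-0.5 is 6-16% without baseline and about 5% with it.

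**The case against.** The strongest reply is that SAP 9.1.2 already supplies baseline. It is a general rule for efficacy analyses, 9.2.4 lies in the efficacy section, and nothing there says baseline is excluded. The shell proves nothing, because the primary ANCOVA shell prints no baseline p-value either. A reader might infer that the SAP deliberately drops baseline, and the documents do not support that. What stands is that 9.2.4 writes its own covariable list without the term, so the text can be programmed either way.

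A reader might also infer that omitting baseline makes the predictive test spurious. With equal slopes it does not. With unequal slopes (assumed baseline-change correlation 0.2-0.35 in placebo, 0.45-0.58 in treated), interaction rejections are 6-14% without baseline and 6-15% with a baseline main effect, so that term is no remedy there. Nor are the 6-28% marker rejections errors in every sense. The marker really is associated with change in those settings, and the finding is false only if the question is whether the marker adds to baseline.

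On timing, a reader might infer that late samples will serve as predictors. No passage says so. Footnote 21 concerns collection, and the aim of prediction points naturally to T1. But nothing rules out a later value. The 20-50% figures need every value to be post-dose and a link in treated subjects only.

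Finally, the main Part 2 comparisons of PDFF and cT1 are baseline-adjusted when the ANCOVA is used, so the treatment column in 9.2.4 is secondary.

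**Conclusion.** The point holds as a minor clarification of an exploratory analysis. SAP 9.2.4 does not carry in the baseline covariate that the general rules call for, and it leaves the marker visit open. The visit is the weightier gap, since no general rule fills it.

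All sizes rest on assumed correlations and 30 per arm. Baseline gives a modest gain in precision, makes the marker p-value conditional on baseline, and protects the Part 2 treatment p-value if baselines differ. The timing harm is conditional: 12-50% in the all-post-dose settings where the assumed links differ by arm, and near 5% where the links are equal.

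The documents do not support requiring a baseline-by-treatment term. No passage calls for it, and it would widen the interaction SE by 5-16% relative to no baseline term if the marker correlates 0.5 with baseline. It is at most an optional sensitivity analysis.

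**What to change.** Amend SAP 9.2.4 as follows.

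- Regress change in PDFF (or cT1) on baseline PDFF (or cT1), the marker value before the first dose, treatment, and marker-by-treatment.
- Use the T1 value for CCR5 and the cytokines. For the FibroTest and biochemistry rows, name one pre-first-dose value in advance: screening, T1 or their mean.
- Apply the same rule to the calcium flux marker added in SAP 10.1, if a pre-first-dose sample exists. Protocol 7.9 and Table 7-1 do not list that assay. The rule is not needed for haplotype if that is a fixed genetic trait.
- Keep subjects with only post-dose CCR5 samples out of the predictive model, describe them separately, and report their number per arm.

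Baseline PDFF and cT1 already come from the screening MRI, so the covariate needs no new data and takes one degree of freedom. The real cost is the loss of subjects without a T1 CCR5 sample. By the formula in step 1, the interaction SE grows by sqrt(27/(n-3)) if n per arm remain: 1.11 times at 25, 1.26 at 20, 1.50 at 15 and 1.96 at 10. The documents do not say how many remain.
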